### Participant and Caregiver Instruction

Each participant and their caregivers will be trained in the following: 1) Self-Trainer placement; 2) Self-Trainer charging and use; 3) Self-Trainer cleaning; and 4) Aspiration precautions. Participants and caregivers will learn to locate the thyroid notch (Adam's apple) and place the motor contacts so that they are on either side of the thyroid notch (Figure 1). Each participant's device attachment cuff will be marked to illustrate where the Velcro should be secured to assure appropriate tightness for a neck pressure that is comfortable but effective for inducing swallowing during vibration. The participant and caregiver will also learn to verify correct placement by phonating while the vibration is on to determine if they can hear the sound of the vibration in their voice to indicate correct placement.

The participant and caregiver will learn the differences between automatic and manual modes and how to change the device to operate in each mode. Verbal, written, and/or video instructions will instruct the participant and caregiver to secure the Self-Trainer to the outside of the participant's neck (as described above) every morning after breakfast with the device set in automatic mode. The participant will wear the Self-Trainer set to automatic mode during waking hours with the exception of mealtimes, swallowing practice and during vigorous exercise when it may be cumbersome to use. The participant will learn to correctly sequence active swallowing practice with the Self-Trainer, which involves the following steps: 1) pushing the button to turn on the device vibration, 2) initiate swallowing within a 1/3 of a second while the vibrator is "on", and 3) releasing the button when the swallow is completed. Participants will be given written, pictorial, and/or video instructions on how to use the device and how to verify correct placement of the device. Instruction and training will be provided on how to daily clean and charge the device. Participants will learn to follow a daily regimen for preventing aspiration of secretions and for preventing aspiration pneumonia including good oral hygiene, monitoring for wet vocal quality, taking their body temperature, and only using the Self-Trainer in an upright position (see Human Subjects Protection).

### Dependent variables:

Data on participant training: Each participant and their caregiver will be asked to demonstrate device setting up and use after each training session. When the participant and caregiver are able to demonstrate appropriate use based

on a checklist completed by the examiner, their training will be completed. The number of training sessions required and total training time before accurate use is demonstrated will be recorded for each participant. The participants will also be asked a series of multiple choice questions about the usefulness of training sessions and training materials.

Outcome measures for documenting swallowing and dietary changes will be taken at baseline and at end of the 3 month self-training period. Outcome measures for all participants will include the following: 1) Training and maintenance data; 2) Participant feedback questionnaire; 3) Participant fidelity data; 4) Modified Barium Swallow administered and scored with the Modified Barium Swallow Impairment Profile Protocol (Martin-Harris et al., 2008) and the 5) Dysphagia Outcome and Severity Scale (O’Neil et al., 1999) with the rater blinded to participant ID and condition; 6) the Dysphagia Handicap Index (DHI) (Silbergbeit et al., 2012); and 7) percent change in hemoglobin oxygenation in the somatosensory and motor regions associated with swallowing and measured with functional near-infrared spectroscopy (fNIRS) as an indirect measure of brain activation changes.

Procedures:

- A. Telephone screening done by speech pathologists in the Laboratory of Neural Bases of Communication and Swallowing
  - a. Telephone screening script (Appendix A); if persons are not excluded at this point, they will be invited to continue enrollment with the informed consent process.
  - b. Participants will be mailed records request to sign and mail to their hospital to obtain medical records for enrollment diagnostic verification. Diagnoses will be confirmed by medical records review before enrollment into the study.
  - c. Participants will also be mailed the informed consent form for information purposes prior to the consenting visit
- B. Informed Consent (Appendix B) and Research Screeners: Consenting appointment can take place at James Madison University’s Laboratory of Neural Bases of Communication and Swallowing or SRMH Voice and Swallowing Service in the Outpatient Center. As all consent and release forms contain participant information (name), these will be stored separately from the de-identified case report forms in a locked cabinet at the James Madison University Neural Bases of Communication and Swallowing Lab. This lab remains locked at all times and allows only authorized keycard entry. Participants who are under 18 will be asked to sign an assent form, which describes the research procedures in grade appropriate language, and their parent/guardian will be asked to sign a parent consent form to allow their child to participate in the research.
  - a. A medical history form will be used to gather background information on the participant’s medical history (Appendix C)
  - b. Eligible participants will read or be read the risks and benefits with the investigators before signing the consent form. Each participant will be provided with a copy of his or her signed informed consent form.
  - c. After signing consent forms, participants will be asked to sign release forms
    - i. Release form: Participants have access to the summarized group data from this research (Appendix D)
    - ii. Release form: Researchers may use their data for educational purposes (Appendix E)
    - iii. Release form: Permission for Future Contact Release Form, Neural Bases of Communication and Swallowing Laboratory (Appendix F)
    - iv. Release form: Permission for Future Contact Release Form, Communication Sciences and Disorders Department (Appendix G)
  - d. Folstein Mini-Mental State Examination (MMSE) will be administered as a screening examination (Appendix H)
  - e. Dysphagia Outcome and Severity Scale (DOSS) (O’Neil et al., 1999) will be administered as a screening examination and allows the speech pathologist to assign a 1 to 7 numerical score to the safest food and liquid consistency that the participant can take orally, ranging from no food restrictions to no oral

intake. As a screening test, the DOSS will be completed by the speech pathologist per discussion with the participant about their current oral intake (Appendix J). This rating scale form will be identified only by ID number with no personal health information. Each participant must obtain a score of 5 or lower, indicating a restricted diet secondary to oropharyngeal dysphagia, to participate in the protocol.

- f. Consented subjects will fill out the Edinburgh Handedness Inventory (Appendix O), a 10 question survey, to determine hand dominance.
- g. Self-Trainer Motor Selection: If the participant has participated in the protocol "The Passy Muir Swallowing Self-Training Device to Enhance Recovery Post Stroke" (IRB 13-0010) then the optimal motor settings for the participant from this study will be used. However, if the participant has not participated in the previous study, then optimal motor settings will need to be identified for that patient. Motors at frequencies ranging from 30-150 Hz and other hybrid motors combining two frequencies (using 2-6 kPa neck pressure) will apply 8 seconds of stimulation followed by 15 seconds of rest for a total of 28 stimulation trials for a total of 10.7 minutes per motor frequency. Using the same vibration time specifications, neck pressure, vibration mode, and vibration duration may also be tested so that optimal motor parameters can be selected for each participant. Online recordings of bi-axial accelerometry of laryngeal motion and inductive plethysmography of respiration will identify laryngeal movement and respiratory apnea to confirm swallows. The rate of swallowing during the 10.7 minute condition will be computed for each motor condition and compared to baseline to identify the optimal motor to use with the patient for daily swallowing self-training during device use. All testing done for motor selection will be video recorded for later analysis. Each digital video file will be saved using the participant's study ID only and will be stored on an encrypted drive for 5 years after publication, after which it will be destroyed.
  - i. Online digitizing with AD instruments Powerlab and Chart software will record accelerometry on the neck measuring laryngeal movement onset and offset and inductive plethysmography noninvasive recordings of chest wall and abdominal respiratory movement to identify swallows and the apneic period. These recordings will be identified only by ID number and stored as Chart files for analysis on encrypted computers or the secure server in the laboratory at JMU accessible by VPN from laptops in the Voice and Swallowing Service. Analyses will be conducted on workstations in the Laboratory of Neural Bases of Communication and Swallowing at JMU and only identified by ID code with no personal health information (PHI).

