Documentation of Dysphagia: Participants will be identified as having swallowing difficulties for admittance into the study by obtaining medical records. Swallowing difficulty will be verified during the modified barium swallow completed as a baseline outcome measure.

Exclusion criteria: Exclusion from this study is contingent on participant self-report of one of the following:

- Ongoing psychiatric disorder for which the patient is receiving medication and is under the care of a psychiatrist
- Epileptic seizure
- Severe speech or language problems affecting communication and reading comprehension
- Cognitive impairment limiting understanding of the consent process and ability to follow directions as assessed by the Folstein Mini-mental State Examination (Folstein et al. 1975) with a score of less than 23.
- Diagnosis of esophageal disorders interfering with the ingestion of food and/or liquid.
- Inability to tolerate a nasal endoscopic exam.
- Rapidly progressive neurological disease such as amyotrophic lateral sclerosis, myasthenia gravis, and progressive supranuclear palsy.

Inclusion criteria:

- Participant must be 13 years old or older
- If the participant is under 18, parental consent must be given

- Stable medical condition
- Diagnosis of oropharyngeal dysphagia confirmed by MBS baseline measure of the following two scales:
  - Penetration-Aspiration Scale score of 2 or greater verified by modified barium swallow (Rosenbek et al., 1996; Appendix I) and/or
  - Functional Oral Intake Scale score of 5 or lower (Crary et al., 2005; Appendix P)
- Folstein Mini-Mental State Examination (MMSE) score of 23 or greater indicating cognitive ability to follow directions and communicate preferences (Appendix H)
- Willingness to travel SRMH2 or more times to undergo initial evaluation, device use training and checkup at 3 months.

Exclusionary Criteria for Participants Who Agree to Undergo MRI and fNIRS:

- Pregnancy
- Cardiac problems
  - history of cardiac rhythm condition (including heart murmur or cardiac arrhythmia)
  - cardiac pacemaker in place
- Highly-pigmented (dark) skin color is an exclusion criterion because near-infrared spectroscopy requires the measurement of the degree of absorption of different wavelengths of light after being reflected back through the scalp. Highly pigmented skin interferes with wavelength transmission, making the measurement of changes in absorption inaccurate.

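### Does leaving the DOSS cut-off out of the inclusion list give the trial two conflicting entry rules?

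*Protocol*

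**What the plan says.** The inclusion criteria, in the protocol section Procedures/Research Design/Methodology/Timeframe, ask for "Diagnosis of oropharyngeal dysphagia confirmed by MBS baseline measure of the following two scales". The two scales are "Penetration-Aspiration Scale score of 2 or greater verified by modified barium swallow" and "Functional Oral Intake Scale score of 5 or lower", joined by and/or. The DOSS is in neither the inclusion nor the exclusion list.

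The DOSS enters later, among the consent and screening procedures (section B, item e). There it "will be administered as a screening examination and allows the speech pathologist to assign a 1 to 7 numerical score", based on a conversation about what the participant currently eats and drinks. The item ends with the rule: "Each participant must obtain a score of 5 or lower, indicating a restricted diet secondary to oropharyngeal dysphagia, to participate in the protocol".

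The step before it (item d) reads "Folstein Mini-Mental State Examination (MMSE) will be administered as a screening examination". That instrument's cut-off does appear in the eligibility lists, twice: as an inclusion criterion, "Folstein Mini-Mental State Examination (MMSE) score of 23 or greater", and as an exclusion, "with a score of less than 23".

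Section D (Outcome measures), item d, names two scores to be taken from each modified barium swallow (MBS) video: the MBSImp and the DOSS.

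**The concern.** Eligibility should be readable from one place. Here a mandatory condition stands only in the procedures, and it is stricter than the list. If PAS alone is enough, a person who penetrates or aspirates on the MBS but eats without restriction meets the list and fails the DOSS screen.

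The omission cannot be put down to a habit of keeping screeners out of the list. Two instruments are called screening examinations; one has its cut-off listed twice and the other not at all.

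The scales that are listed also look unsupported. Neither PAS nor FOIS is among the scores taken from the MBS video, and neither appears among the data points under Data Analysis. No procedure step says when FOIS is rated. FOIS cites an Appendix P, while the list of attachments ends at O.

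At stake is the description of the study population. With 12 to 20 participants, the entry rule largely settles whom the results describe, and a reader of the list alone would describe a wider group than the one enrolled.

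**Working it through.** The protocol gives no figure to reproduce, so the check is one of logic.

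**Inputs.** Rule A (inclusion list): PAS ≥ 2 and/or FOIS ≤ 5. Rule B (section B, item e): DOSS ≤ 5, required of everyone.

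**Step 1: can both rules hold together?** Each scale is passed or failed, which gives 2 × 2 × 2 = 8 patterns. With *and/or* read as *or*:

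| Pattern | PAS ≥ 2 | FOIS ≤ 5 | DOSS ≤ 5 | Rule A | Rule B | Both |
|---|---|---|---|---|---|---|
| 1 | yes | yes | yes | pass | pass | enrol |
| 2 | yes | no | yes | pass | pass | enrol |
| 3 | no | yes | yes | pass | pass | enrol |
| 4 | no | no | yes | fail | pass | no |
| 5 | yes | yes | no | pass | fail | no |
| 6 | yes | no | no | pass | fail | no |
| 7 | no | yes | no | pass | fail | no |
| 8 | no | no | no | fail | fail | no |

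Rule A passes 6 patterns, Rule B passes 4, and both together pass 3. If *and/or* is read as *and*, Rule A passes 2 (patterns 1 and 5) and both together pass 1. These are counts of patterns, not of people.

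**Step 2: do the rules contradict each other?** They would if one required the enrolment of someone the other bars. Patterns 5 to 7 fail Rule B, and Rule A nowhere says that meeting the list is sufficient. Pattern 4 fails Rule A, and Rule B nowhere says that the DOSS is sufficient. Every pattern has one answer when both rules are applied.

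**Step 3: does the order of events cause trouble?** The DOSS screen belongs to the consent stage; the MBS is a baseline outcome measure. Someone screened out on the DOSS would normally not reach the study MBS, so no study PAS would exist to set against the refusal. Pattern 6 is mostly a case on paper.

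**Step 4: are PAS and FOIS without a home?** The inclusion criterion ties both to the baseline MBS, and the PAS form is listed as Appendix I. The score list in section D concerns outcomes. PAS and FOIS are entry criteria, so their absence there, and from the outcome data points, is expected. What remains is that FOIS has no rating step of its own and its appendix is missing from the index.

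**Step 5: is the direction of the DOSS unclear?** Sections B and D describe the 1 to 7 scale as going from an unrestricted diet to nothing by mouth, without saying which end is 1. The cut-off sentence settles it: 5 or lower means a restricted diet.

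**The case for a change.** The strongest reply is practical. Data Analysis says the case report form templates will require the inclusion and exclusion criteria. A form built from the list alone would leave out the DOSS gate and ask for a FOIS value that no step produces. Telephone screening also works from the inclusion criteria, so people might be invited and then refused after signing consent. And since the DOSS is an outcome as well as an entry threshold, readers should be able to see that entry was capped on it.

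Part of this stands. The list is incomplete, the combined rule is not written in one place, and a line for the DOSS and another for the FOIS rating would be good housekeeping.

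The rest carries less weight. The forms are not shown, so it is unknown whether they omit the gate, and section B provides a DOSS rating form for each participant in any case. Refusal after consent is not peculiar to the DOSS: the MMSE and the baseline MBS also come after the telephone call. The cap on the DOSS operates, and is stated in the protocol, whether or not the list repeats it. The outcome DOSS is a separate rating, made from the MBS with participant and condition masked.

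**Conclusion.** The concern is accurate about the text but calls for no change to the plan. The inclusion list leaves out a condition that the protocol states bindingly elsewhere. Read as a whole, the protocol gives one coherent rule: PAS of 2 or more and/or FOIS of 5 or less, together with DOSS of 5 or less. Repeating the DOSS line in the list would admit nobody new and exclude nobody who is not already excluded. It would alter no analysis, estimate or conclusion.

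This rests on two assumptions: that staff apply the screening step as written, and that the list is not meant to be exhaustive, which the protocol never says it is. The number of people with PAS 2 or more and an unrestricted diet cannot be estimated, because the protocol gives no such rate; under the rule as written they are not enrolled whatever that number is. The baseline DOSS is recorded, so the severity of those enrolled will show in the data. The missing FOIS rating step, the Appendix P reference and the loose wording of the DOSS range are clerical.

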#### C. Training session

- a. The participants will be trained on appropriate device placement, appropriate device pressure, how to verify correct placement of the device, and how to use the device daily for swallowing therapy. Caregivers will be encouraged to attend to provide support and will be trained to "coach" the participant.
- b. Self-Trainer guides will be given to the participant in the following forms:
  - i. Written directions with pictures
  - ii. Optional DVD instructional video
- c. Once the participant and their caregiver can demonstrate correct use of the Passy Muir Self Trainer for Swallowing, they will be given the device to take home and use for 3 months. The investigators will provide phone support to the participant and caregivers every day for the first 3 days of participation and on a weekly basis after that. The participants and caregivers will be encouraged to call the investigators with questions as needed and the investigators will be available for one on one meetings as needed. All contacts will be documented.

#### D. Outcome measures

Outcome measures a-e will be completed at the SRMH Voice and Swallowing Services in the Treatment Center. Voice and Swallowing Service is a collaboration between SRMH Healthcare and James Madison University.

- a. Training and maintenance data will be taken on each participant and will include how many training sessions were required to demonstrate competency for device use, the duration of each training session, caregiver involvement, documentation of questions or comments during maintenance phone calls, and how many times the participant contacted the research team and for what purposes.
- b. Participant feedback will be gathered at the end of the 3 month self-training period. The participant will read or be read a series of multiple choice questions (Appendix K) regarding their opinion on the training they received, ease of device use, and design of the device. The participants will be instructed to answer truthfully and will be assured that their answers will not impact their treatment or enrollment in this or future research studies at JMU/SRMH.
- c. Participant fidelity will be measured by 1) daily documentation by the participant or caregiver on device use and 2) downloading the count data from the device periodically throughout the study which provides data on how many times the device has vibrated in automatic mode and in manual mode.
- d. Modified Barium Swallow study (MBS) will be completed in radiology and requires the participant to swallow small amounts of barium. This will be done by a licensed speech-language pathologist who has been trained to complete MBS. An MBS study will be completed at baseline and after the 3 month self-training period. During each exam the participant will swallow thin liquid, nectar thick liquid, honey thick liquid, puree, and solid texture (cracker/cookie). For the entire MBS protocol, see Appendix L. The participant will be given each consistency in gradually increasing amounts from 5 ml to approximately 15 ml (See Human Subjects Protection). If more than a trace amount of aspiration is observed on any trial, the remaining trials of that consistency will be discontinued from the study. Radiation exposure time for each study will be 5 minutes or less. All MBS studies will be recorded for later analysis. All recordings will be de-identified with a random ID number. Each MBS study will include a 19 mm metal sphere calibration marker be taped to the side of the neck for future displacement measures. Each video will be analyzed for:
  - i. Modified Barium Swallow Impairment Profile score (MBSImp) (Martin-Harris et al., 2008) allows the speech pathologist to rate specific physiological movement during each swallow and assign an overall 0 to 55 numerical score representative of swallowing impairment in the oral, pharyngeal, and esophageal phase (Appendix L).
  - ii. Dysphagia Outcome and Severity Scale (DOSS) (O'Neil et al., 1999) allows the speech pathologist to assign a 1 to 7 numerical score to the safest food and liquid consistency that the participant can take orally, ranging from no food restrictions to no oral intake. The DOSS will be completed by the speech pathologist while reviewing each MBS while participant ID and condition will be masked (Appendix J). This rating scale form will be identified only by ID number with no personal health information.
- e. Dysphagia Handicap Index (DHI) (Silbergbeit et al., 2012) survey requires the participant to rate their agreement with 25 statements pertaining to their swallowing (Appendix M). The DHI is designed to determine how the patient's swallowing affects their day to day quality of life on a physical, functional, and emotional level and possible scores range from 0-100. The DHI will be completed by the participant with help from the caregiver or speech pathologist as needed. The DHI will be completed at baseline, after the 3 month self-training period, and at 1 month post the self-training period. This survey will be identified only by ID number with no personal health information.
- f. Magnetic Resonance Imaging: Some participants may be scheduled to receive an MRI scan at SSRMH as a part of the study. The MRI image can be used to identify the 3 dimensional locations of particular regions of the brain from the scalp position and can also provide information as to the anatomical location of brain tissue damage, for example, if the patient has had a stroke or brain injury. MRI scans will be conducted at SRMH on a 1.5 Tesla MRI, to allow fNIRS recording from corresponding anatomy.

Female participants who are pregnant cannot undergo a research MRI scan. Although there have not been any reports of injury to a fetus from MRI, we want to prevent any unforeseen difficulties when these scans are being performed for research purposes and are not needed for patient care. Female

participants who have child bearing potential will need to undergo pregnancy testing prior to MRI scanning. To decide whether a female participant has child bearing potential, we will also ask each female participant the date of their last menses in order to determine whether they are post-menopausal. Any female participant who is over 1 year since her last menses will be considered post-menopausal (unless they are breastfeeding) and not have child bearing potential and will not require a pregnancy test. All female participants who have child bearing potential (i.e. are not post-menopausal) will be given a pregnancy test kit by the JMU research team (free of charge) and will be asked to take the pregnancy test the morning before going to the SRMH for their MRI scan. They must report to the research staff at JMU that the test was negative before going for their MRI scan. If participants have not reported a negative pregnancy test before a scan, the scan will be cancelled by the JMU staff by contacting the SRMH. Results of the pregnancy test will be confidential and discussed privately with the participant alone, even if the participant is a minor. Participation in the MRI will not be essential for participating in the study.

g. Functional Near-Infrared Spectroscopy (fNIRS) will be conducted on those participants willing and able to travel to James Madison University Neural Bases of Communication and Swallowing Laboratory for testing prior to device use and after 3 months of device use. Therefore, fNIRS data may not be taken on every participant. fNIRS will be used to measure the hemodynamic response in the brain while the participant is asked to actively swallow, recording cortical activation changes in the primary motor cortex and somatosensory cortex bilaterally during swallowing in comparison with rest. Participation in the fNIRS will not be essential for participating in the study.

- i. This is a noninvasive technology using optodes to emit laser lights, similar to pulse oximetry in concept and practice. Light detectors are placed 3 centimeters from the emitters to absorb any reflected light from the emitter. These emitters and detectors are placed on the scalp after parting the hair to reduce inference from pigment in hair. The only risk to participants and the investigative team is if the emitters are turned on and a laser light could be shined in someone's eyes, similar to laser pointers. Therefore, the emitters will only be turned on after they are placed and attached to a participant's scalp. The lasers will be turned off prior to moving or replacing the emitters on the scalp. Six emitters and ten detectors will be attached to the scalp over 6 locations with Coban material, a self-adhesive stretching material similar to an Ace bandage, which will be wrapped over the optodes and detectors to keep them in place. Bobby pins and clips will be used to part the hair when appropriate, a non-invasive procedure. No hair will be cut and any color markings made on the scalp for the Brainsight identified coordinates will wash off in the shower with shampoo.
- ii. fNIRS data files will be deidentified and saved for later analysis. fNIRS sessions will be video recorded and saved for future analysis. Each digital video file will be saved using the participant's study ID only and will be stored on an encrypted drive for 5 years after publication, after which it will be destroyed.

E. Participants will return to the SRMH Voice and Swallowing Service at the end of the 3 month self-training period to document outcome measures as outlined in section C. If the participant has also opted to participate in fNIRS, they will also return to the James Madison University Neural Bases of Communication and Swallowing Laboratory at 3 months.

F. Follow up and Discharge:

- a. During months 4-6 the investigators will contact the participant by phone or Skype one time each month to follow up on their progress and answer any questions. At the end of month 6, the participant will be mailed the Dysphagia Handicap Index survey (Appendix M) to complete and return by mail and a statement of discharge from the study (Appendix N). The participant will be encouraged to contact the investigators if they should have questions or concerns in the future.

Potential Problems and Alternative Strategies: Anticipated problems include difficulties with recruiting an adequate sample of patients in the Harrisonburg area for testing in our clinic at SRMH. A website has been developed for promoting research on the swallowing Self-Trainer (swallowingselftrainer.com), which can be used by the public, speech pathologists or participants, to educate themselves on the uses of the Self-Trainer or to get contact information. Advertisements on Google and on the National Foundation of Swallowing Disorders are also in place to help with recruitment. In this manner, participants who are interested in swallowing research can self-refer. Also participants who have participated in a previous protocol involving the Self-Trainer and have stated that they give permission for future contact will be contacted for participation in this study. Participants can also be recruited from the SRMH/JMU Voice and Swallowing Service, the SRMH/JMU Swallowing Support Group, which meets bimonthly as well as other dysphagia services in the area, including other local support groups. Local speech-language pathologists will be informed of current research projects and will be able to inform their patients to contact us for more information.

Statistical Analysis: Questionnaire data will be categorized and coded. Quantitative data will be analyzed using Analysis of Variance (MANOVA) for repeated measures with a Bonferroni corrected alpha of 0.05.

